2.1 Study Objectives

To investigate differences in allocated urgency level when emergency calls are dispatched by emergency medical service (EMS) utilizing video streaming as opposed to sole telephone (audioonly) communication. Secondary aims include the association between the use of video streaming and secondary and exploratory endpoints listed below.

2.2. Study period

The study will be conducted from January 1, 2023, to April 30, 2023.

2.3 Study setting and cluster design

In the Central Denmark Region, a single Emergency Medical Dispatch Center (EMDC) handles all emergency calls (equivalent to 9-1-1 calls in the US). The region receives approximately 55,000 to 60,000 emergency calls annually and employs around 25 Emergency Medical Service (EMS) Dispatchers, all of whom are either nurses or paramedics. Within the EMDC, EMS dispatchers were divided into one of two clusters, each containing 10 EMS dispatchers. Due to the limited number of clusters, a matched-pair (MP) design was adopted. This design relied on specific criteria for matching, including the average proportion of dispatched urgency levels (with the highest urgency level as the primary criterion), years of employment, and the average call duration. The data used for matching covered a 3-month period from January 1, 2022, to March 31, 2022, both prior to the introduction of video streaming and preceding the pilot phase of the study.

Newly employed personnel where matching was not possible were randomly assigned to one of the two clusters. Before the study period, the implementation of video streaming in the intervention group occurred progressively over a span of 7 months (from June 1, 2022, to December 31, 2022), following a pilot phase that took place from April 19, 2022, to May 31.

2.4 Endpoints

Primary Outcome Measure

• The frequency of dispatches with the highest level of urgency (A-responses)

Secondary Outcome Measures

- The frequency of dispatches with the levels of urgency A, B, C, D and E,
- Mortality within 30 days after study inclusion,
- Number of participants where the levels of urgency are identical when comparing the ambulance

to and from the scene,

SAP version 1.0: CAM-VISION

- Length of stay at hospital,
- The number of participants needing an ICU admission at hospital,
- Number of emergency calls where the dispatched level of urgency is changed during the call,
- Number of emergency calls where the initially dispatched level of urgency is subsequently lowered,
- Number of emergency calls where the initially dispatched level of urgency is subsequently increased,
- Number of emergency calls where the allocated resources is changed during the call,
- Number of participants readmitted to hospital within 24 hours after a dispatch without hospital admission (lowest level of urgency response level E),
- Duration of emergency medical calls,
- Time from emergency call to dispatch,
- On-scene time

Other Pre-specified Outcome Measures:

- Number of participants with return-of-spontaneous circulation (ROSC) after cardiac arrest
- 90 days neurological outcome after cardiac arrest measured by the cerebral performance scale (CPC)
- 90 days functional outcome after cardiac arrest measured by the modified Rankin Scale (mRS)
- Number of patients with Stroke or TIA identified by the EMS dispatcher in the EMDC
- Rate of revascularization treatment (intravenous thrombolysis and/or endovascular treatment (EVT)) among patients with acute ischemic stroke
- Primary admission to a hospital offering acute stroke treatment
- Onset-to-treatment times for patients with acute ischemic stroke treated with i.v. thrombolysis and onset-to-groin-puncture for patients treated with EVT.
- Number of lowest level of urgency (response level E) dispatched among children (< 15 years

of age)

SAP version 1.0: CAM-VISION

- Re-admissions among children (< 15 years of age) to hospital within 24 hours from a prior emergency call dispatched with lowest level of urgency (response level E)
- Number of dispatches for each level of urgency (response level A, B, C, D and E) among children (< 15 years of age)

3 Study Methods

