3.3 Randomization

Emergency calls will be allocated at random to either of the two clusters: the intervention group utilizing video, or the control group utilizing telephone-only communication. Alternatively, some emergency calls will be directed to EMS dispatchers who are not part of the study.

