3.6 Analysis Populations

Intention to Treat (video stream)

The intention-to-treat populations (intension-to-video-stream) includes all patients allocated to either exposure group. Binary outcomes are investigated using risk differences (RD) implementing linear regression and relative risks (RR) by Poisson regression. Robust variance estimation is applied in both regression analyses. Continuous outcomes are investigated using linear and Tobit regression, where the latter is implemented for time variables that are right censored. Time-to-event variables are SAP version 1.0: CAM-VISION 18.08.2023 Page 6 of 7

investigated using Cox-regression analysis, while CPC and mRS are investigated using ordered logistic regression and by the concordance index. To account for cluster randomization, we will implement cluster robust variance in all regression analyses with a separate cluster id for each EMS dispatcher. Effect measures are presented with 95% confidence intervals and all analyses are conducted in Stata 17.

No per-protocol analyses will be conducted because of substantial risk of selection bias.

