3.7 Missing Data

The anticipated connection between treatment allocation and loss to follow-up is expected to be minimal. Thus, missing data, including outcomes, is assumed to be missing at random and will be handled using multiple imputation.

The extent of missing data will be presented for outcome variables to quantify the degree of missing data.

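### The stroke time endpoints start at symptom onset, so they carry a delay fixed before allocation that costs precision; call-based times should be added or the delay adjusted for

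*SAP*

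**What the plan says.** SAP section 2.4, under "Other Pre-specified Outcome Measures", defines the stroke time endpoints as "Onset-to-treatment times for patients with acute ischemic stroke treated with i.v. thrombolysis and onset-to-groin-puncture for patients treated with EVT". Both clocks start at symptom onset.

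Section 3.3 sets the point of allocation: "Emergency calls will be allocated at random to either of the two clusters". Section 3.1 says the same of calls received at the dispatch centre.

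The time outcomes in section 2.4 that start at or after the call are the length of the call, the time on scene and "Time from emergency call to dispatch". None runs from the call to thrombolysis or groin puncture.

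For analysis, section 3.6 says "Continuous outcomes are investigated using linear and Tobit regression, where the latter is implemented for time variables that are right censored", with "cluster robust variance in all regression analyses with a separate cluster id for each EMS dispatcher". It names no covariate for onset-to-call time.

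**The concern.** Onset-to-treatment time is the sum of onset-to-call and call-to-treatment time. A patient enters the comparison only when the call is allocated, so the dispatcher can affect only the second part. The first part carries no treatment signal. If it varies independently of the second, its variance is simply added to the outcome and passes into the confidence interval.

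These are the plan's only measures of whether video shortens the time to stroke treatment. If onset-to-call time varies widely, a null result on them would say little about that question, even where a call-based time from the same patients would have been informative.

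**Working it through.** **The plan's own figure.** The only relevant number in the SAP is the expected 18,000 to 20,000 calls (section 3.4). Section 2.3 says "The region receives approximately 55,000 to 60,000 emergency calls annually". Over the 120 study days, 55,000 × 120/365 = 18,082 and 60,000 × 120/365 = 19,726. Taking 4/12 of a year gives 18,333 and 20,000. The figure reproduces, but it does not bear on this point, because the SAP gives no number of treated strokes, no SD and no expected effect for these endpoints.

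**Assumptions.** Onset-to-call SD a = 15, 30, 60 or 90 min. Call-to-treatment SD b = 20 or 30 min. Independent parts, a 10 min effect, 100 treated patients per arm, two-sided 5% level and no clustering. None of these comes from the SAP.

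**Formulas.**
- Onset-based SD: S = √(a² + b²)
- Variance ratio: S²/b² = 1 + (a/b)²
- Power: Φ(10 / (S√(2/100)) − 1.96)
- n per arm for 80% power: 2 × (1.96 + 0.84)² × S² / 10²

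Example with b = 20 and a = 15: S = √(225 + 400) = 25. The variance ratio is 625/400 = 1.56. Power is Φ(10/(25 × 0.1414) − 1.96) = Φ(0.87) = 81%.

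| b (min) | a (min) | S (min) | Variance ratio | SD ratio | Power | n per arm, 80% power |
|---|---|---|---|---|---|---|
| 20 | call-based | 20.0 | 1.00 | 1.00 | 94% | 63 |
| 20 | 15 | 25.0 | 1.56 | 1.25 | 81% | 99 |
| 20 | 30 | 36.1 | 3.25 | 1.80 | 50% | 205 |
| 20 | 60 | 63.2 | 10.00 | 3.16 | 20% | 628 |
| 20 | 90 | 92.2 | 21.25 | 4.61 | 12% | 1,335 |
| 30 | call-based | 30.0 | 1.00 | 1.00 | 65% | 142 |
| 30 | 15 | 33.5 | 1.25 | 1.12 | 56% | 177 |
| 30 | 30 | 42.4 | 2.00 | 1.41 | 38% | 283 |
| 30 | 60 | 67.1 | 5.00 | 2.24 | 18% | 707 |
| 30 | 90 | 94.9 | 10.00 | 3.16 | 11% | 1,413 |

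A larger effect can survive. With a 20 min effect, b = 20 and a = 30, power from onset is still 98%.

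**Correlated parts.** With correlation r, the variance ratio is 1 + (a/b)² + 2r(a/b).
- For a = 60, b = 30 and r = −0.3: 1 + 4 − 1.2 = 3.8, an SD ratio of 1.95 against 2.24 under independence.
- The ratio falls to 1 when r = −a/(2b). For a = 15 and b = 30 that is r = −0.25, so at the mild end a modest negative correlation would cancel the loss.

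**Clustering.** Variation between dispatchers would sit in the call-to-treatment part. Assume 10 patients per dispatcher, an intracluster correlation of 0.05 in that part only, a = 60 and b = 30.
- Call-based: 900 × (1 + 9 × 0.05) = 1,305
- Onset-based: 3,600 + 1,305 = 4,905
- SD ratio: √(4,905/1,305) = 1.94, again against 2.24

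**Effect of adjustment.** In a linear model with onset-to-call time as a covariate, the arm coefficient is the same whether the outcome is onset-based or call-based, because the two outcomes differ only by that covariate. Ignoring clustering, the residual variance is b²(1 − r²), which never exceeds b². Adjustment therefore recovers the precision whatever the sign of r.

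**The case against.** Onset-to-treatment time is a coherent interval, and nothing else in the SAP contradicts it. The endpoints are in the lowest tier, no power claim attaches to them, and section 3.5 places them after the primary and secondary outcomes. Preferring a more sensitive clock could be called a matter of taste. The low priority stands. It does not remove the point, because the plan otherwise has no precise comparison of stroke treatment times, and the remedy needs no new data.

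Four stronger readings are tempting, and the SAP does not support them:

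- **Any dispatch effect is lost in noise.** This needs SDs, an effect size and a count of treated strokes. The SAP gives none, and the assumed range runs from a mild loss to a severe one.
- **The comparison is biased.** With random allocation the delay before the call is balanced in expectation, so this mechanism costs precision only. Restriction to treated patients could disturb that balance, but it is a separate limitation that affects both clocks.
- **Outcomes with unknown onset will be imputed.** Section 3.7 does say "missing data, including outcomes, is assumed to be missing at random and will be handled using multiple imputation". The SAP does not say how onset is defined or how often it is unknown, so no weight can rest on this.
- **The onset-based endpoints should be replaced.** Section 3.5 says the study and follow-up periods had already ended when the SAP was drafted. Dropping or demoting a pre-specified outcome then would cost credibility, and adding a call-based time makes it unnecessary.

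**Conclusion.** The point holds as an inefficiency in how these endpoints are fixed. Both stroke times include a part that ends before allocation, and the plan neither lists a call-to-treatment time nor adjusts for that part.

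Under the assumed SDs and independence, the variance is inflated 1.25 to 21 times. For a 10 min effect with 100 treated per arm, power falls from 94% to between 81% and 12% (b = 20), or from 65% to between 56% and 11% (b = 30). Dispatcher clustering or negative correlation would reduce the loss, and at the mild end negative correlation could remove it. Positive correlation would increase it.

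Primary and secondary conclusions do not depend on these endpoints.

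**What to change.** Keep both onset-based endpoints. Then do one of the following:

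1. Add the time from emergency call to start of thrombolysis and the time from emergency call to groin puncture, and name these as the between-arm comparison of the stroke pathway.
2. Adjust the onset-based times for onset-to-call time in the regression of section 3.6.

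Under option 1, say which timestamp marks the call and which call counts when a patient has more than one. Under option 2, the same definition is needed for the covariate.

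The cost is wording. The call time is already needed for the call-to-dispatch outcome, and the onset and treatment times for the existing stroke endpoints. Section 3.5 says data extraction had not begun when the SAP was drafted, so the change could be made before any data were seen. If extraction has since started, the amendment should be dated and say so.

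Neither option removes the selection from timing only treated patients, while the revascularization rate is itself an outcome in section 2.4. The report should state that limitation.

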3.1 General Study Design and Plan

Study type: Single center, prospective, cluster-randomized, unblinded trial.

Type of Comparison: superiority

Type of control: Matched control group (matched-pair design)

Randomization: Emergency calls received in the Emergency Medical Dispatch Center are allocated

randomly between the intervention group and the control group. Given the extended call duration

within the intervention group, it is anticipated that the control group (telephone-only) will experience

a higher volume of calls.

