3.4 Sample Size

The CAM-VISION trial is conducted using a convenience sample, with an anticipated count of emergency calls during the study period ranging between 18,000 and 20,000.

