3.5 Timing of Analyses

The study period and its corresponding follow-up periods, as determined by specific variables, are finalized during the drafting of this SAP (Statistical Analysis Plan).

As of this SAP, data extraction has not been initiated due to pending data authorization. The subsequent actions, in chronological order, prior to data extraction and analysis, are outlined below:

SAP Signature

• By the principal investigator and the senior statistician.

Data Authorization

- The Regional Research Council (The Legal Office, Central Denmark Region) and
- The Danish Data Protection Agency.

Primary Analyses

• Primary and Secondary Outcomes

Secondary analyses

Other Outcomes

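### Calls are probably routed among free dispatchers, yet the primary RD and RR models name no time-of-call covariate; adding one is a cheap improvement, and no material bias is shown

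*SAP*

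**What the plan says.** SAP 3.3 states: "Emergency calls will be allocated at random to either of the two clusters"; some calls go instead to dispatchers outside the study. SAP 3.1 also calls the allocation random. It then expects that, since calls take longer "within the intervention group, it is anticipated that the control group (telephone-only) will experience" a larger volume. No allocation ratio or routing rule is given.

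SAP 2.3 puts 10 dispatchers in each arm. They are matched on baseline urgency-level proportions (A-responses first), length of employment and mean call duration, using January to March 2022 data. Shift or roster is not a criterion. "Newly employed personnel where matching was not possible were randomly assigned to one of the two clusters".

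SAP 3.6 states: "Binary outcomes are investigated using risk differences (RD) implementing linear regression and relative risks (RR) by Poisson regression". Variance is clustered by dispatcher in every regression. No covariate is named for either model.

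**The concern.** If each call were sent to an arm with a fixed probability, call length could not change the number of calls per arm. The shift expected in 3.1 makes sense if a call goes to someone who is free. A video dispatcher is then occupied for longer, and the video arm receives a smaller share of calls when traffic is heavy. The arms would therefore differ slightly in their mix of busy and quiet periods. They could also differ if their dispatchers work different shifts.

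If the proportion of A-responses varies over the day or with load, the unadjusted RD and RR contain a little of that variation along with the video effect. Clustering by dispatcher changes the standard error but leaves the point estimate as it is.

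**Working it through.** **1. The plan's own figure.** SAP 2.3: "The region receives approximately 55,000 to 60,000 emergency calls annually". The study period in 2.2 is 120 days. 55,000 × 120/365 = 18,082 and 60,000 × 120/365 = 19,726. This agrees with SAP 3.4: "an anticipated count of emergency calls during the study period ranging between 18,000 and 20,000".

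**2. Model for the load part.** Poisson arrivals, exponential call lengths, random choice among free lines, calls finding no free line dropped, equal time in quiet and busy periods.
- From the SAP: 55,000-60,000 calls a year, which is 0.105-0.114 per minute.
- Assumed: 4-minute control calls; video calls 20-50% longer; 2-3 lines per arm on duty; busy:quiet rate ratio 3.7.
- Rates per minute, quiet/busy: 0.0445/0.1648 (55,000 a year) and 0.0486/0.1797 (60,000 a year).

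The exact stationary solution gives control 50.6-52.4% of calls, in the direction 3.1 expects. The difference between arms in the share of calls from busy periods (control minus video, in points) is:

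| Calls a year | 3 lines, +20% | 3 lines, +50% | 2 lines, +20% | 2 lines, +50% |
|---|---|---|---|---|
| 55,000 | 0.32 | 0.80 | 0.52 | 1.27 |
| 60,000 | 0.35 | 0.88 | 0.56 | 1.37 |

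**3. Bias in the RD** = difference in busy share × A-share gap between busy and quiet periods (gap assumed).
- 10-point gap: 0.32 × 0.10 = 0.03 to 1.37 × 0.10 = 0.14 points.
- 20-point gap: 0.06 to 0.27 points.

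**4. Yardstick.** Call-level SE = sqrt(4p(1−p)/N). This is 0.65 points (N = 20,000, assumed A-share 30%) to 0.75 points (N = 18,000, A-share 50%). Clustered SE = call-level SE × sqrt(1 + (N/20 − 1) × ICC), with an assumed ICC of 0.001-0.01. This is 0.92 to 2.36 points. The largest biases are:
- 0.14/2.36 = 0.06 to 0.14/0.92 = 0.15 clustered SE (10-point gap);
- 0.27/2.36 = 0.12 (from the unrounded 0.274) to 0.27/0.92 = 0.30 clustered SE (20-point gap).

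Coverage of a nominal 95% interval is Φ(1.96 − k) − Φ(−1.96 − k): 94.7% at k = 0.15 and 94.0% at k = 0.30.

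**5. Sensitivity to handling time.** With 12 minutes, 2 lines, +50% and 60,000 calls, the busy-share difference is 2.87 points. At a 20-point gap the bias is 2.87 × 0.20 = 0.57 points, which is 0.57/2.36 = 0.24 to 0.57/0.92 = 0.62 clustered SE. At k = 0.62 coverage is about 90%. A wider grid (3-20 minutes, video calls up to twice as long, rates 0.5 and 1.5 times the mean) reaches 0.50 points at a 10-point gap and 1.0 at 20. In the other direction, one added non-study line at 4 minutes lowers the differences to 0.27-1.07 points.

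**6. Roster part.** The SAP gives no split of calls by shift. The imbalance in busy-period share that would move the RD by one clustered SE is SE/gap:
- 10-point gap: 0.92/0.10 = 9 to 2.36/0.10 = 24 points;
- 20-point gap: 5 to 12 points.

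These are thresholds, not estimates.

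**7. Possible gain in precision.** Suppose dispatchers' busy-period shares have SD s and the A-share gap is g. The unadjusted RD then carries extra variance 2(sg)²/10, with 10 dispatchers per arm.
- s = 5 points, g = 0.10: sqrt(2 × 0.5²/10) = 0.22 points.
- s = 10 points, g = 0.20: sqrt(2 × 2²/10) = 0.89 points.

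If the SE without this component is 0.92, removing it shortens the interval by 1 − 0.92/sqrt(0.92² + 0.22²) = 3% or 1 − 0.92/sqrt(0.92² + 0.89²) = 28%. If that SE is 2.36, the same sums give 0.4% and 6%. Both s and g are assumed.

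**The case against.** The strongest defence is that nothing in the SAP is misstated. Random choice among free dispatchers is compatible with both 3.1 and 3.3, and 3.1 discloses the volume shift openly. The routing mechanism may be described in a protocol that is not at hand. A reader might infer that the SAP contradicts itself on randomisation. The text does not support that, and this part of the defence stands.

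A reader might also infer that the primary estimate is materially biased by rosters. No section indicates that the arms' rosters differ. Newcomers without a match were assigned at random, so any imbalance among them is chance. Matching on baseline A-proportion absorbs persistent shift differences among the others, though not roster changes since early 2022. If dispatchers were randomised, clustering by dispatcher carries chance imbalance into the interval. This stands too.

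It is also fair to say that an unadjusted analysis is legitimate in a randomised trial, and that the SAP gives no evidence that the A-share varies by hour. That limits the point to an improvement. It does not remove it, because choosing covariates for the primary model is the SAP's job and the adjustment uses only information fixed before a call is allocated.

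**Conclusion.** The point holds as a minor improvement to the analysis. The expected volume shift implies availability-based routing, which is a sound inference but not a stated rule, and the RD and RR models take no account of time.

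The load-driven bias is small under the assumed inputs: 0.03-0.27 points with 4-minute calls, up to about 0.6 points with 12-minute handling and a 20-point A-share gap. It is not bounded by the SAP, which gives no handling time, staffing on duty, A-share by period or ICC. Time spent on other calls is left out of the model. Direction is unknown: control receives relatively more busy-period calls, so the RD (video minus control) is pushed down if busy periods have the higher A-share and up if they have the lower. The roster part cannot be sized.

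**What to change.** In 3.6, prespecify hour-of-day band (for example three bands) and weekday/weekend, both fixed at call arrival, as covariates in the primary RD and RR models. Report the unadjusted estimate alongside.

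**Cost.** A sentence or two and about three parameters (two for the bands, one for weekday/weekend). The timestamps are already needed for the duration and time-to-dispatch outcomes. SAP 3.5 records that "data extraction has not been initiated due to pending data authorization", so at the SAP's date this could be fixed without sight of results. If extraction has since begun, the amendment should say so.

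**Gain.** Most between-period variation is removed from the comparison and, if rosters differ between dispatchers, the dispatcher-clustered interval is narrower.

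**Downsides.** Three more parameters with about 20 clusters; bands capture momentary load only partly; and there is some overlap with the matching, which used raw A-proportions that already contain each dispatcher's shift mix.

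**Optional clarifications.** State in 3.1 and 3.3 that call allocation depends on availability, or refer to the protocol if it describes routing. Tabulate calls by arm and hour band in 3.8.
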